8.2.6. Mental Health Questionnaires

8.2.6.1. Columbia Suicide Severity Rating Scale (C-SSRS)

The C-SSRS is an interview-based rating scale to systematically assess suicidal ideation and suicidal behavior.¹⁸ The "baseline/screening" version of the C-SSRS will be administered at V1. The "since last visit" version of the C-SSRS will be administered at the other visits specified in the SoA for the applicable cohort (see SoA for Cohorts 1 and 2, and SoA for Cohort 3). The C-SSRS will be administered by study site staff who have completed training in its administration. Participants who respond "yes" to questions 4 or 5 (indicating suicidal ideation), or to any suicidal behavioral question on the C-SSRS at V1, V2 or V3 will not be permitted in the study (see Section 5.2).

8.2.6.1.1. Rater Qualifications

For specific rating assessments, only qualified raters will be allowed to evaluate and/or rate participants in this study. The minimum qualifications a rater must meet will be outlined in a guidance document provided to each participating site. The level of experience with the target population (or equivalent), specific scale experience (or equivalent), and certification required (if applicable) will be listed and used to determine whether a rater is approved for a given assessment. The rater must become certified to perform selected study assessments before he or she can participate in the conduct of the study. For specifically defined assessments, rater training and standardization exercises may be conducted, and written and signed documentation will be provided by the site for each rater's certification. In return, each site will be provided written and signed documentation outlining each rater's certification for specific study assessments. Recertification may be required at periodic intervals during the study. The raters who administer specific study assessments will be documented in a centralized location and all site staff who administer ratings will be verified in the site study documentation during the conduct of the study.

8.2.6.2. Patient Health Questionnaire-9 (PHQ-9)

The PHQ-9 is a 9 item self-report scale for the assessment of depressive symptoms. ¹⁹ The PHQ-9 will be completed by participants and reviewed by site staff at the pre-defined time points outlined in the SoA for the applicable cohort (see SoA for Cohorts 1 and 2, and SoA for Cohort 3). A PHQ-9 score of ≥15 at V1, V2 or V3 indicates clinically significant depression and serves as an exclusion criterion for this study (see Section 5.2).

8.2.6.3. Referral to a Mental Health Professional

A participant should be referred to a MHP for any of the following reasons:

- Response of "yes" to question 4 or 5, or on any behavioral question on the C-SSRS;
- A score of \geq 15 on the PHQ-9;
- In the investigator's judgment a risk assessment or exclusion is required.

A clinically-qualified MHP is a MHP with appropriate training in the assessment of suicide risk, according to local clinical practice standards and regulations, who would normally evaluate the risk for suicidal ideation and behavior in a patient.

Participants who have recurrent suicidal ideation or behavior during the study should be discontinued from the study and treated appropriately. If a study participant endorses a 4 or 5 on the ideation subscale or any behavioral item of the C-SSRS on 2 or more occasions and is confirmed to have active suicidal ideation or behavior on both occasions by a risk assessment conducted by a qualified MHP, then the participant should be discontinued from the study and treated appropriately.

Participants who meet criteria for referral to a MHP, but refuse evaluation and/or treatment by a MHP, must be assessed by the investigator to determine if the participant should be discontinued from dosing or from the study.

8.2.7. Pregnancy Testing

Pregnancy tests will be both urine and serum, and must have a sensitivity of at least 25 mIU/mL. Pregnancy tests will be performed in all females at the times listed in the SoA for the applicable cohort (see SoA for Cohorts 1 and 2, and SoA for Cohort 3). Following a negative pregnancy test result at screening, appropriate contraception must be commenced and a second negative pregnancy test result will be required at the baseline visit prior the participant's receiving the study intervention. Pregnancy tests will also be done whenever 1 menstrual cycle is missed during the active treatment period (or when potential pregnancy is otherwise suspected) and at the end of the study. Pregnancy tests may also be repeated if requested by IRBs/ECs or if required by local regulations.

8.3. Adverse Events and Serious Adverse Events

The definitions of an AE and an SAE can be found in Appendix 3.

AEs will be reported by the participant (or, when appropriate, by a caregiver, surrogate, or the participant's legally authorized representative).

The investigator and any qualified designees are responsible for detecting, documenting, and recording events that meet the definition of an AE or SAE and remain responsible to pursue and obtain adequate information both to determine the outcome and to assess whether the

event meets the criteria for classification as an SAE or caused the participant to discontinue the study intervention (see Section 7.1).

Each participant will be questioned about the occurrence of AEs in a nonleading manner.

In addition, the investigator may be requested by Pfizer Safety to obtain specific follow-up information in an expedited fashion.

8.3.1. Time Period and Frequency for Collecting AE and SAE Information

The time period for actively eliciting and collecting AEs and SAEs ("active collection period") for each participant begins from the time the participant provides informed consent, which is obtained before the participant's participation in the study (ie, before undergoing any study-related procedure and/or receiving study intervention), through and including a minimum of 28 calendar days after the last administration of the study intervention.

Follow-up by the investigator continues throughout and after the active collection period and until the AE or SAE or its sequelae resolve or stabilize at a level acceptable to the investigator.

For participants who are screen failures, the active collection period ends when screen failure status is determined.

If the participant withdraws from the study and also withdraws consent for the collection of future information, the active collection period ends when consent is withdrawn.

If a participant permanently discontinues or temporarily discontinues study intervention because of an AE or SAE, the AE or SAE must be recorded on the CRF and the SAE reported using the CT SAE Report Form.

Investigators are not obligated to actively seek AEs or SAEs after the participant has concluded study participation. However, if the investigator learns of any SAE, including a death, at any time after a participant has completed the study, and he/she considers the event to be reasonably related to the study intervention, the investigator must promptly report the SAE to Pfizer using the CT SAE Report Form.

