1.3. Schedule of Activities (SoA)

PROCEDURES section of the protocol for detailed information on each procedure and assessment required for compliance with the protocol. The investigator may schedule visits (unplanned visits) in addition to those listed in the SoA table, in order to conduct The SoA table provides an overview of the protocol visits and procedures. Refer to the STUDY ASSESSMENTS AND evaluations or assessments required to protect the well-being of the participant.

1.3.1. SoA for Cohorts 1 and 2

| Protocol Activity (See Appendix 11 for abbreviations) | Scree Ph | Screening Phase | | | | • • | Freatment Phase | ent Ph | ase | | | | End of Treat- ment ^a | Follow-up ^b | | Early Term/ Dis- |
|--|-------------|--------------------|------------------|----------|----------|----------|-----------------|----------|----------|----------|----------|---------------|---------------------------------------|------------------------|-----------|--------------------------------|
| ¥2 | Screen | Pbo run-in | | | | | | | | | | | | | o n | contin- uation ^c |
| Study Parth | | | | | | Part A | t A | | | | | Part B | | | | |
| Weeks Relative to Dosing on Day 1 | | | 0 | 2 | 4 | 9 | 8 | 10 | 12 | 16^{a} | 18 | 22 | 26 | 27-28 | 30-31 | ET |
| Days Relative to Dosing on Day 1 ^d | -42 | -14±3 | 1 | 14±3 | 28±3 | 42±3 | 26±3 | 70±3 | 84±3 | 112±3 | 126±3 | 154±3 | 182±3 | 189- | 210- | |
| | cl- 01 | | 71. | 1 | ; | } | ; | , | , | 0.52.5 | 777. | - | 977. | - | 717 | |
| Visit | V1 | V2 | V3 | V4 | VS | 9A | V7 | 8. | 60 | V10 | V11 | V12 | V13 | V14 | $V15^{e}$ | |
| Informed consent & demography | X | | | | | | | | | | | | | | | |
| Review of eligibility criteria | X | X | x | | | | | | | | | | | | | |
| Medical history | X | | | | | | | | | | | | | | | |
| SF-36v2® (all sites) ^f | | X | X | | | | | | | X | | | X | | | |
| PGI-S (US only) ^f | | X | X | X | X | X | Х | X | X | X | X | Х | X | | | |
| PROMIS®, IWQOL-Lite-CT® (US only) ^f | | X | X | | | | | | | X | | | Х | | | |
| PGI-C (US only) ^f | | | | | X | | | | | Х | | | Х | | | |
| Open-ended inquiry for AEs | X | | \uparrow | ↑ | ↑ | ↑ | ↑ | ↑ | ↑ | ↑ | ↑ | \rightarrow | ↑ | ↑ | X | х |
| Review prior/concomitant treatments | х | X | X | X | X | Х | X | X | Х | X | X | Х | Х | X | X | X |
| Review drug, alcohol, tobacco use | Х | X | х | X | X | х | X | X | X | Х | X | Х | Х | X | X | X |
| Review contraception use (females only) | Х | X | Х | X | X | х | X | X | X | Х | X | Х | X | X | X | X |

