| Blood sampling for: | | | | | | | | | | | | | | | | |
| Hematology, Chemistry (including FPG and eGFR) | × | | × | × | × | × | × | × | × | X | × | × | X | × | | × |
| FSH (females only); C-peptide | X | | | | | | | | | | | | | | | |
| Pregnancy test (all females) ^o | X | X | X | X | X | Х | X | X | X | X | X | X | X | X | | X |
| HbA1c | X | | X | | | | | | | Х | | | X | | | X |
| Lipids, TSH, free T4, calcitonin, amylase, lipase, TBA, PT/INR/aPTT, FPI | X | | x | | х | | × | | x | x | | х | х | x | | × |
| PF-06882961 PK (pre-dose unless noted) | | | X^{m} | | X | | X^{m} | X | | X^{m} | | | \mathbf{x}^{m} | | | X |
| Banked biospecimen: Prep B1 & B2 | | | X | | | | | | | X | | | X | | | X |
| Banked biospecimen: Prep D1 (only Day 1) ⁿ | | | X | | | | | | | | | | | | | |
| Urine Sampling for: | | | | | | | | | | | | | | | | |
| Urine drug screen | X | | | | | | | | | | | | | | | |
| Urinalysis (and microscopy, reflexive) | X | | X | | X | | X | | X | Х | | Х | Х | Х | | X |
| On-site urine pregnancy test (all females)° | | × | X | × | × | × | × | × | × | X | X | X | X | × | | X |

PFIZER CONFIDENTIAL CT02-GSOP Clinical Protocol Template Phase 1 2 3 4 (05 December 2019) Page 24

- Final Protocol Amendment 2, 16 September 2022
- a. **End of Treatment:** Defined as Week 26.
- Study part and Follow-up: In Part A (Weeks 1-16) participants will be randomized and dosed with double-blinded study intervention on Day 1 and dosing will continue through 16 weeks. In Part B (Weeks 17-26) participants in Part A will continue dosing, according to randomization from Part A.
- Early termination/discontinuation: This visit applies only to participants who are enrolled/randomized and then are prematurely withdrawn from the study, ie, permanently discontinued both from the study intervention and from the study. Note: discontinuation of study intervention does not represent withdrawal from the study. If only study intervention is discontinued, the participant will remain in the study and continue with all visits and assessments (except for dosing activities and assessment of PK). See ပ
- Days relative to Dosing on Day 1: Dosing occurs on Day 1 and timing of subsequent visits is determined by adding the number of days noted to Day 1. For example, V4 is Day 1+14 days (± 3 days), V5 is Day 1+28 days (± 3 days), etc. ġ.
- e. Follow-up V15: Visit may be a phone call. f. Site based PROs: Completed at the site on

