| Protocol Activity (See Appendix 11 for abbreviations) | Screening Phase | ning ase | | | | | | | Tre | Treatment Phase | ıt Pha | se | | | | | | | | | Early Term/ |
|---|---------------------|---------------|---------------------------|------------|----------|----------|----------|------------|-------------|-----------------|----------|----------|-----------------|------------------|-------------|--------------|-------------|---------------------------------------|-------------|-------------|---|
| | Screen Pbo run-i | Pbo run-in | | | | | | | | | | | | | | | | End of Treat- ment ^a | | Follow-up | Dis- cont- inua- tion ^b |
| Weeks Relative to Dosing on Day 1 | | | 0 | 2 | 4 | 9 | ∞ | 10 1 | 12 1. | 14 16 | | 18 2 | 20 2 | 22 24 | t 26 | 5 28 | 30 | 32 | 33- 34 | 36-37 | ET |
| Days Relative to Dosing on Day 1° | -42 to -15 | -14±3 | 1 | 14± 3 | 28± 4 | 42± 5 | 56±3 7 | 70± 8, | 84± 98 3 | 98±3 112± | | 126± 14 | .40± 154 3 3 | 154± 168 3 ±3 | 8 182± | 2± 196 ±3 | 6 210± | 224±3 | 231- 238 | 252- 259 | |
| Visit ("T" denotes telephone contact) ^d | V1 | V2 | V3 | V4- T | NS V | -9A T | V7 \ | V8- V T | V9 V1 T | V10- V11 T | > | | V13 V14 T | .4- V15 | 5 V16- T | 6- V17 | 7 V18- T | - V19 | V20 | V21- T | |
| Informed consent & demography | × | | L | | | H | | H | \vdash | H | \vdash | \vdash | H | H | H | H | L | L | L | | Г |
| Review of eligibility criteria | Х | X | X | | | | | | | | \vdash | | \vdash | | | | | | | | |
| Medical history | х | | | | | | | | | | | | | | | | | | | | |
| SF-36v2® (all sites) ^e | | X | X | | | | | Н | | X | | H | Н | Х | | | | х | | | |
| PGI-S (US only) ^e | | X | Х | | Х | | X | . , | х | Х | | - | х | X | | X | | Х | | | |
| PROMIS®, IWQOL-Lite-CT® (US only) | | X | X | | | | | | | X | | Н | Н | X | | | | х | | | |
| PGI-C (US only) ^e | | | | | X | | | Н | H | X | | Н | Н | х | | | | х | | | |
| Open-ended inquiry for AEs | х | ↑ | ↑ | ↑ | 1 |  | ↑ |  | 1 | ↑ | _ |   |   | ↑ | 1 |  | 1 | ↑ | \uparrow | х | х |
| Review prior/concomitant treatments | х | X | Х | X | X | X | X | X | x | X X | | X > | x x | X | X | X | X | X | Х | X | Х |
| Review drug, alcohol, tobacco use | X | X | х | | X | | x | | х | X | | 7 | x | X | | x | | X | X | х | Х |
| Review contraception use (females only) | х | X | X | X | X | X | X | X | x | X X | Н | X Y | X X | X | X | × | X | x | X | X | Х |

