| Weeks Relative to Dosing on Day 1 | | | 0 | 2 | 4 | 9 | 8 | 10 | 12 | 0 2 4 6 8 10 12 14 16 18 20 22 24 26 28 | 5 18 | 3 20 | 22 | 24 | 26 | 28 | 30 | 32 | 33- 36-37 | 6-37 | ET |
| | | | | | | | | | | | | | | | | | | | 34 | | |
| Days Relative to Dosing on Day 1 ^c | -42 to | -42 to -14±3 | 1 | 14± | 78∓ | 12± 5 | €∓9 | 8 ∓0∠ | 1 14± 28± 42± 56±3 70± 84± 98±3 | 3 112 | £ 126 | ± 140 | ± 154 | ± 168 | 3 182 | ₹ 196 | 210± | 112± 126± 140± 154± 168 182± 196 210± 224±3 | 231- 252- | 252- | |
| | -15 | | | 3 | 3 | 3 | | 3 | 3 | 3 | 3 | 3 | 3 | ±3 | 3 | ±3 | 3 | | 238 | 259 | |
| Visit ("T" denotes telephone contact) ^d | V1 | V2 | V3 | V4- | . SA | -9/ | V7 \ | 87 | V9 V | V3 V4- V5 V6- V7 V8- V9 V10- V11 V12- V13 | 1 V1 | 2- V1 | 3 V1 | 1- V1; | 5 V16 | - V17 | V14- V15 V16- V17 V18- | V19 | V20 V21- | V21- | |
| | | | | Τ | | Τ | | T | | T | T | | T | | Ι | | \mathbf{I} | | | Τ | |
| On-site urine pregnancy test (all | | X | X | | X | | х | | X | X | | Х | | Х | | X | | х | x | | X |
| females) ¹ | | | | | | | | | | | | | | | | | | | | | |

- End of Treatment: Defined as Week 32
- Early termination/discontinuation: This visit applies only to participants who are enrolled/randomized and then are prematurely withdrawn from the study, ie, permanently discontinued both from the study intervention and from the study. Note: discontinuation of study intervention does not represent withdrawal from the study. If only study intervention is discontinued, the participant will remain in the study and continue with all visits and assessments (except for dosing activities and assessment of PK). See
- Days relative to Dosing on Day 1: Dosing occurs on Day 1 and timing of subsequent visits is determined by adding the number of days noted to Day 1. For example, V4-T is a telephone contact at Day 1+14 days (±3 days), V5 is an in-clinic visit at Day 1+28 days (±3 days), etc ပ
- Visit: Visits with a "T" are planned as telephone contacts, while other visits are planned as in-clinic study visits. .
- Site based PROs: Completed at the site on an electronic tablet. Participants at ex-US sites will only complete the SF-36v2. assessments (SF-36v2®, PGI-S, PGI-C, PROMIS® Fatigue, PROMIS® Physical Function, IWQOL-Lite-CT®). See Section 8.1.3 for more details. ij

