4.4. End of Study Definition

A participant is considered to have completed the study if he/she has completed all phases of the study, including the last follow-up visit, approximately 28 to 35 days post last dose of study intervention.

The end of the study is defined as the date of the last visit of the last participant in the study across all sites globally.

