Morning dosing will occur at the site with food at V2-V13 for Cohorts 1 and 2 (see SoA for Cohorts 1 and 2), and at scheduled in-clinic study visits for Cohort 3 (see SoA for Cohort 3). Participants will be instructed to arrive at the site in the fasted state for each of these visits. Participants will be instructed to bring their study intervention supply and dosing diary with them, and to delay self-administration of study intervention until directed to dose during their visit. When participants dose at the site, they will self-administer the study intervention under supervision by site staff. Onsite dosing will be administered from newly dispensed study intervention, with the exception of the End of Treatment visit (ie, the last dose), which will be administered from study intervention supply brought back to the site by the participant, as no new study intervention is dispensed at the End of Treatment visit. The date and time of each dose administered at the site will be recorded in the site source documents, in the diary and in the CRF. Additionally, the date and time of the previous 2 doses of double-blinded study intervention prior to each of the pre-dose PK blood collections (ie, the 2 most recent doses prior to the visit as noted in the diary) will be entered in the CRF.

The actual titration schemes for PF-06882961 to be used in this study are provided in Table 1 for Cohorts 1 and 2, and Table 2 for Cohort 3. Details regarding dose titration are provided in the IP Manual.

Table 1. Titration and Dosing Schemes for Cohorts 1 and 2

| | | Arm 1 | Arm 2 | Arm 3 | Arm 4 | Arm 5 | Arm 6 | Arm 7 | Arm 8 | Arm 9 |
|--------------------|--|---------|-------|--------------|-------------------|--------|--------|--------------|------------------|--------|
| | Cohort 1 | X | x | x | X | x | X | X | X | X |
| | Cohort 2 | X | | | | | | X | X | X |
| | Target | Placebo | 40 mg | 80 mg | 120 mg | 160 mg | 200 mg | 120 mg | 160 mg | 200 mg |
| Study | Dose ^a Study | | BID | BID PF 06 | BID 6882961 (m | BID | BID | BID PF 06 | BID 882961 (m | BID |
| Part | Week | | | | ek Titration | | | 2-wee | k Titration | Steps |
| | 1 | 0 | CCI | | | | | | | |
| | 2 | 0 | | | | | | | | |
| | | | | | | | | | | |
| | 3 | 0 | | | | | | | | |
| | 4 | 0 | | | | | | | | |
| | 5 | 0 | | | | | | | | |
| | | 0 | | | | | | | | |
| 9 | 6 | | | | | | | | | |
| 1 = 2 | 7 | 0 | | | | | | | | |
| eek | 8 | 0 | | | | | | | | |
| Š | 9 | 0 | | | | | | | | |

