8.2.4. Clinical Safety Laboratory Assessments

See Appendix 2 for the list of clinical safety laboratory tests to be performed and the SoA for the applicable cohort (see SoA for Cohorts 1 and 2, and SoA for Cohort 3) for the timing and frequency. All protocol-required laboratory assessments, as defined in Appendix 2, must be conducted in accordance with the laboratory manual and the SoA for the applicable cohort (see SoA for Cohorts 1 and 2, and SoA for Cohort 3). Unscheduled clinical laboratory measurements may be obtained at any time during the study to assess any perceived safety issues.

The investigator must review the laboratory report, document this review, and record any clinically relevant changes occurring during the study in the AE section of the CRF. Clinically significant abnormal laboratory findings are those which are not associated with the underlying disease, unless judged by the investigator to be more severe than expected for the participant's condition.

All laboratory tests with values considered clinically significantly abnormal during participation in the study or within 28 to 35 days after the last dose of study intervention should be repeated until the values return to normal or baseline or are no longer considered clinically significant by the investigator or medical monitor.

If such values do not return to normal/baseline within a period of time judged reasonable by the investigator, the etiology should be identified and the sponsor notified.

See Appendix 6 for suggested actions and follow-up assessments in the event of potential DILI.

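### The final safety contact is counted from Day 1 rather than from the last dose, so an in-window contact can fall 25 to 27 days after dosing, short of the 28-day minimum

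*Protocol*

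**What the plan says.** Section 8.3.1 of the protocol sets active AE and SAE collection for each participant "through and including a minimum of 28 calendar days after the last administration of the study intervention". It names two earlier end points: screen failure, and withdrawal from the study with consent for further information also withdrawn.

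For participants who stay on treatment, Section 6.1.1 puts the final dose at the End of Treatment visit: "Onsite dosing will be administered from newly dispensed study intervention, with the exception of the End of Treatment visit (ie, the last dose"). The SoA places that visit at Day 182 ± 3 in Cohorts 1 and 2 and Day 224 ± 3 in Cohort 3. The final contact is V15, opening at Day 210, or V21-T, at Day 252 to 259. The Cohort 3 row reads "224±3 | 231- 238 | 252- 259" for End of Treatment, V20 and V21-T. In both SoAs, "timing of subsequent visits is determined by adding the number of days noted to Day 1".

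Two other sections use the last dose as the reference point. Section 4.4 defines study completion as "including the last follow-up visit, approximately 28 to 35 days post last dose of study intervention". Section 8.2.4 applies its repeat-test rule to abnormal values seen during participation or "within 28 to 35 days after the last dose of study intervention".

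The early termination (ET) visit is for participants "prematurely withdrawn from the study, ie, permanently discontinued both from the study intervention and from the study". Those who stop only the drug keep all visits (Sections 7.1 and 7.2.1).

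**The concern.** The safety minimum and the visit schedule run on different clocks. The last dose moves with the End of Treatment window, but the window for the final contact does not move with it. If End of Treatment is late and the contact is made on the first days of its window, every SoA window is respected and the 28-day minimum is still missed.

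New events in the last 1 to 3 days of the required period might then go unasked. In the SAP, the main tables of treatment-emergent AEs (365-day lag, SAP 3.2.2.1) and the weekly incidence and prevalence tables that run to follow-up (SAP 6.3.1.2 and 6.3.1.3) draw on this period. The subset tables, which stop two days after the last dose (SAP 3.2.2.1.2), do not.

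A related question concerns participants withdrawn from both drug and study who have not withdrawn consent. The legible SoA text lists nothing for them after ET.

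**Working it through.** **Inputs**
- Required interval: at least 28 days after the last dose (8.3.1).
- Last dose: at End of Treatment (6.1.1), so Day 179 to 185 or Day 221 to 227 (SoA).
- Final contact: Day 210 to 217 (V15) or Day 252 to 259 (V21-T). The upper edge of V15 is garbled in the available text. Day 217 is assumed from the Weeks 30-31 label (31 × 7 = 217).

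**Formula.** Gap = final-contact day − End of Treatment day. Both are counted from Day 1, so the day-numbering convention cancels.

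**Step 1: the plan's own figure.** With End of Treatment on its nominal day:
- Cohorts 1 and 2: 210 − 182 = 28 and 217 − 182 = 35.
- Cohort 3: 252 − 224 = 28 and 259 − 224 = 35.

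This reproduces the 28 to 35 days of Section 4.4 exactly.

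**Step 2: apply the ±3 days.**
- Shortest gap: 210 − 185 = 25 and 252 − 227 = 25.
- Longest gap: 217 − 179 = 38 and 259 − 221 = 38.

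**Step 3: count the permitted pairs.** There are 7 End of Treatment days × 8 contact days = 56 pairs in each schedule.

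| End of Treatment | Contact days giving at least 28 | Short gaps |
|---|---|---|
| On time or early | 8 of 8 | none |
| 1 day late | 7 of 8 | 27 |
| 2 days late | 6 of 8 | 26, 27 |
| 3 days late | 5 of 8 | 25, 26, 27 |

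Short pairs: 1 + 2 + 3 = 6 of 56 (27 days in three, 26 in two, 25 in one). Of the other 50, 44 fall at 28 to 35 days and 6 at 36 to 38.

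**Step 4: sensitivity to the assumed upper edge.** An upper edge for V15 of Day 216, 217, 218 or 219 gives 6 short pairs of 49, 56, 63 or 70. The six do not change, because they all lie in the first three days of the window.

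**Step 5: two possible repairs.**
- Contact at the actual last dose + 28 to 35 days: gap 28 to 35 by construction.
- Keep the Day 1 count and open the windows at Day 213 and Day 255: 7 × 5 = 35 pairs, shortest 213 − 185 = 28, longest 217 − 179 = 38. None is short, but 6 of 35 exceed 35 days, and the contact window shrinks from 8 days to 5.

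**Step 6: early terminators.** Days without a scheduled inquiry = 28 − (ET day − last-dose day), not below 0, so 0 to 28 per person. The documents do not give the number of such people.

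**The case against.** The strongest reply is that nothing here forces a breach. The SoA calls itself an overview and sends the reader to the assessments section, where the 28-day minimum stands. Section 4.4 repeats the interval from the last dose. At least 5 of the 8 contact days comply even in the worst case, and a site that calls at 25 days is breaking Section 8.3.1, not following the protocol exactly. All of that stands, and it rules out calling the provisions irreconcilable. It does not remove the point: the stated window lists Day 210 or 252 as acceptable, and no SoA text seen tells the site to move the contact when End of Treatment was late.

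A reader might also read 6 of 56 as an 11% chance of a short interval. The documents give no distribution of visit days, so it is only a count.

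A reader might further infer that early terminators are proven to have no safety follow-up. The documents do not support that:
- The ET footnote breaks off at its cross-reference in both SoAs in the available text, so a contact rule may stand there.
- Section 8.3.1 exempts only those withdrawals in which consent is also withdrawn.
- Sections 7.1 and 7.2.1 have sites record separately whether a participant is leaving drug, procedures or follow-up.
- Section 8.3.3 keeps recorded events under follow-up.
- Section 10.1.8 asks for appropriate therapy and/or follow-up if the study is stopped.
- Section 1.3 adds: "The investigator may schedule visits (unplanned visits) in addition to those listed in the SoA table".

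Against this, Section 8.3.1 also says that events need not be actively sought once participation has concluded. The legible parts of 7.1, 7.2 and 8.3.1 contain no contact after ET, and unplanned visits are optional. The text pulls both ways, which justifies a clarification but not a finding of a gap.

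**Conclusion.** The point holds as a minor window misalignment. For participants dosed through End of Treatment, the SoA permits a final contact 25 to 27 days after the last dose, a shortfall of 1 to 3 days, in 6 of 56 day pairs in each schedule. It needs a late End of Treatment visit together with an early final contact. There is no effect on efficacy, and no difference by arm is shown. The result rests on the last dose being taken at End of Treatment and on the legible opening days of the final windows; the assumed Day 217 does not affect it.

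The early-terminator point is secondary and conditional on the missing footnote text. If no rule stands there, it concerns a narrow group. Of the reasons in Section 7.2, refusal of follow-up, loss to follow-up and death leave nobody to contact. That leaves mainly withdrawals at the investigator's discretion for safety or behavioral reasons, and termination by the sponsor.

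**What to change.** 1. For participants dosed through End of Treatment, time V15 and V21 at the actual last dose + 28 to 35 days. This matches Section 4.4 and removes all six short pairs. Opening the present windows at Day 213 and Day 255 is not recommended, because it leaves contacts at up to 38 days and a narrower window.
2. Check the full ET footnote. If it holds no contact rule, state in Sections 7.2 and 8.3.1 and in both SoAs that the 28-day minimum still applies to early terminators who have not withdrawn consent. Meet it with one AE phone call at least 28 days after the last dose.

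The cost is an edit to the SoA and case report form windows and at most one call per contactable early terminator. No clinic visit is added, since V15 may already be a call and V21 is one. Changes to the study design need ethics approval (Section 10.1.1), so the window edit is best carried in the next amendment made for other reasons. The amendment history shows that the sponsor has issued administrative clarification letters before. Such a letter could remind sites in the meantime that the 28-day minimum governs the choice of contact day.
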